### **Rules of early stop**

This study also employs two rules for early stopping of the study.

1. Stop the trial if the lowest dose (250 mg) is eliminated due to overt toxicities.
2. Stop the trial and estimate the MTD if the number of new patients treated at the current dose level reaches 15.

### **Determination of MTD**

After the trial is completed, we determine the MTD based on the isotonic regression as specified in Yuan et al[5]. The determined MTD is the dose for which the isotonic estimate of the toxicity rate is closest to the target toxicity rate of 30%. If there are ties, we select the higher dose level when the isotonic estimate is lower than the target toxicity rate; and we select the lower dose level when the isotonic estimate is greater than the target toxicity rate.

The parameters of BOIN design, operating characteristics and sensitivity analysis are described in the protocol.

### **Definition of DLTs**

DLTs are side effects of a drug or other treatment that are serious enough to prevent an increase in dose or level of that treatment during the **first cycle (first 4 weeks)** of treatment.

Common Toxicity Criteria for Adverse Events (CTCAE) 4.0 are used for grading of toxicities in this study.

### **The definitions of DLT include:**

- Grade-4 nonhematologic toxicities;
- Grade $\geq$ 3 febrile neutropenia;
- Any grade-3 non-hematologic toxicities lasting more than 3 days despite of optimal supportive care;
- Grade-3 nonhematologic laboratory abnormalities that persist more than one week and require medical intervention or hospitalization;
- Grade-4 thrombocytopenia requiring platelet transfusion or leading to life-threatening bleeding event.
- Grade-4 neutropenia  $>$  7 days.

### **Treatment cycle and route of administration:**

Each cycle consists of 4 weekly intravenous infusions at the assigned dose level.

Patients with good tolerability and disease control will continue treatment until disease progression or up to the maximum of one year, withdrawal from study or death, whichever comes first. If the individual patient still benefits from the Investigational Product after one year of treatment, extending the treatment beyond one year may be arranged with the Sponsor.

### **Pre-medications**

Primary prophylaxis for first infusion reaction of HLX06 is NOT mandatory. If the patients experience infusion reactions, allergic reactions, nausea, vomiting or other symptoms/signs related to infusion of experimental drugs, pre-medications to mitigate these reactions with antihistamine, acetaminophen, corticosteroid or 5-HT3 antagonist or by institutional guidelines are permitted in subsequent infusions. Infusion time is two hours.

### **Treatment evaluation**

RECIST criteria 1.1 will be used for treatment evaluation.

1. For the first 24 weeks, treatment evaluation is conducted every 8 weeks (i.e. every 2 cycles) despite treatment delay.
2. After 24 weeks, treatment evaluation is conducted every 12 weeks (3 cycles).

### **Dose modification scheme**

Dose modification is based on the toxicities from previous infusions. Patients who experience reversible DLTs **are** allowed to receive additional infusions at the next lower dose level, provided that the toxicities have reverted to grade≤1 in 28 days after last infusion, and that the patients still meet the inclusion criteria for adequate organ functions.

*For patients who experience DLTs, re-escalation to the dose level that causes DLT is not permitted. Up to two dose-level reductions per patient are allowed in this study.*

### **Pharmacokinetic studies**

To measure the serum concentration of HLX06, blood samples will be collected pre-dose (within one hour), immediately after infusion (within 30 minutes), and at 2, 4, 8, 24, 48, 96, and 168 hours from the 1st and 4th infusion in cycle 1.

Additional time points include pre-dose and after 2nd and 3rd infusions (30 minutes allowable) in cycle 1. Thereafter, the blood levels of HLX06 will be measured before the first infusion of cycle 2 to cycle 6 or up to 24 weeks, whichever comes first; on the 28-day follow-up visit, whenever possible.

Non-compartmental pharmacokinetic analysis will be used to estimate the PK parameters.

### **Pharmacodynamic studies**

Serum concentrations of VEGF-A, soluble VEGFR-1, soluble VEGFR-2 will be measured before and after each infusion in cycle 1 in conjunction with pharmacokinetic studies.

### **Immunogenicity studies**

---

 For patients with hepatocellular carcinoma, mRECIST is used to evaluate treatment effect[6]

[figure not shown]
Serum samples used to evaluate the presence of antibody against HLX06 will be obtained prior to every infusion of HLX06 in cycle 1 and before the first infusion in subsequent 5 cycles or up to 24 weeks, whichever comes first; at the end of therapy, and at the 28-day follow-up visit, whenever possible.

**Table 1. Dose escalation table**

No. of patients treated at current dose level	3	6	9	12	15
Escalate if # of DLT	0	1	2	3	3
Remain at the same dose if # of DLT	1	2	3	4	4,5
De-escalate if # of DLT	2	3	4	5	6
Eliminate if # of DLT	3	4	6	7	8

The rules to escalate or de-escalate are as follows:

- (a) “Eliminate” means that we eliminate the current and higher doses from the trial to prevent treating any future patients at these doses because they are overly toxic.
- (b) When we eliminate a dose, we automatically de-escalate the dose to the next lower level. When the lowest dose is eliminated, we stop the trial for safety. In this case, no dose should be selected as the MTD.
- (c) If none of the actions (i.e., escalation, de-escalation or elimination) is triggered, we treat the new patients at the current dose.
- (d) If the current dose is the lowest dose and the rule indicates dose de-escalation, we will treat the new patients at the lowest dose unless the number of DLTs reaches the elimination boundary, at which point we will terminate the trial for safety.
- (e) If the current dose is the highest dose and the rule indicates dose escalation, we will treat the new patients at the highest dose up to maximum 30 patients.
- (f) If the number of new patients treated at the current dose reaches 15, stop the trial and determine the MTD based on data from enrolled patients.

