### **Study design**

This study employs the modified accelerated titration design (ATD) 2A[1] and Bayesian optimal interval design (BOIN) to assign patients in the study cohort and identify MTD.

ATD 2A design assumes that the toxicities and effects increase monotonically with doses. It starts with a rapid initial escalation phase by using cohorts of a single new patient to lower the probability of exposing patients to sub-therapeutic doses.[1] When moderate-to-severe toxicities emerge at higher doses, the acceleration phase ends and the study returns to cohorts with 3 new patients.

The BOIN design is a novel adaptive dose-finding method that allows dose escalation and de-escalation and estimates the posterior probability of toxicity rate using updated information [2]. This design is considered to have higher probability of identifying the MTD.

**Dose levels and sample size:** 250, 500, 750, 900, 1200, 1500 mg (flat dose, with no adjustment of body weight or body surface area)[3]. A maximum of 30 patients will be enrolled in the phase 1 study. Patients who withdraw from the study during the first cycle due to reasons not related to treatment-emergent toxicities will be replaced.

Dose escalation sequence is modified from the Fibonacci sequence.

**Determination of starting dose and its dose levels:** the starting dose is **500** mg (flat dose), which is at dose level 2 and approximately equal to 1/6 of human equivalent dose of highest non-severely toxic dose (HNSTD) in the *cynomolgus* study[4].

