#### 11.1.2. Operating characteristics

The following table (Table 2) shows the operating characteristics of the proposed design for this trial with 6 scenarios defined by different DLT rates for 6 dose levels. These operating characteristics are based on 1000 simulations of the trial using the acceptable toxicity range [0.21, 0.39]. The operating characteristics show that the design selects the true MTD with high probabilities and allocate more patients to the dose levels with the DLT rate close to 0.3.

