**Table 2 Operating Characteristics of the BOIN design**

Toxicity range	Dose level						Number of pts	% early stopping
	1	2	3	4	5	6		
[0.21, 0.39]	True DLT rate	0.05	0.10	0.30	0.45	0.60	0.8	
	Selection %	0.3	18.9	58.5	20.0	2.3	0	27.7
	# pts treated	3.6	7.2	10.9	5.2	0.8	0	
[0.21, 0.39]	True DLT rate	0.12	0.30	0.46	0.60	0.70	0.9	
	Selection %	21.2	57.7	19.0	1.7	0.2	0	25.1
	# pts treated	7.4	11.2	5.6	0.9	0.1	0	
[0.21, 0.39]	True DLT rate	0.26	0.50	0.65	0.75	0.80	0.9	
	Selection %	73.1	18.2	0.3	0	0		20.1
	# pts treated	12.4	6.7	0.9	0	0		
[0.21, 0.39]	True DLT rate	0.05	0.10	0.16	0.30	0.50	0.7	
	Selection %	0.2	2.7	23.7	55.7	17.1	0.6	29.2
	# pts treated	3.7	4.7	7.3	9.1	3.9	0.4	
[0.21, 0.39]	True DLT rate	0.02	0.03	0.05	0.12	0.30	0.45	
	Selection %	0	0.1	0.6	19.9	55.7	23.7	29.8
	# pts treated	3.2	3.4	3.8	6.7	8.5	4.3	
[0.21, 0.39]	True DLT rate	0.5	0.65	0.75	0.80	0.90	0.95	
	Selection %	35.8	0.5	0	0	0	0	11.3
	# pts treated	10	1.3	0	0	0		63.7

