## 15.6. R codes used to derive the dose escalation and de-escalation

Table 1 is generated with software R 3.4 with BOIN package 2.4. Various scenarios of toxicity distribution with target toxicity rate at different dose levels are generated with dfcrm package.

Operative characteristics of the study design are also generated with BOIN package.

The R script for this study is as follows:

```
if(!require("pacman")){
  install.packages("pacman")
  pacman::p_load(BOIN, dfcrm)
  target<-0.3 # target toxicity rate#
  nc<-10 #number of cohorts
  cs<-3 # cohort size
  nes<- 15 # number of pts in a cohort for early stop#
  sb<-target*0.7 #set up the safe boundary, narrower than default#
  tb<-target*1.3 #set up the toxic boundary,narrower than default#
  get.boundary(target=target,ncohort=nc, cohortsize = cs, n.earlystop = nes, p.saf =sb, p.tox = tb,
  extrasafe = FALSE, offset = 0.05)

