  # get operating characteristics
  # use dfcrm to get priors
  delta<-0.09 # the acceptable range of DLT
  mtd0<-3 # prior MTD, usu. the starting dose#
  k<-6 # number of dose levels
  p0<-getprior(halfwidth=delta, target=target, nu=mtd0, nlevel=k, model = "empiric")
  p1<-round(p0, digits = 2)
  p1 # the toxicity probability distribution
  get.oc(target = target, p.true = p1, ncohort = nc, cohortsize = cs, n.earlystop = nes, p.saf = sb,
  p.tox = tb, extrasafe = FALSE, ntrial = 1000) # get operative characteristic
```

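### Table 1 eliminates a dose at 6 DLTs in 9 patients, but the stopping rates in Table 2 are those of a rule that eliminates at 5 in 9

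*Combined protocol and SAP*

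**What the plan says.** Table 1 in the Synopsis gives the DLT counts at which a dose and all higher doses are closed. The row "Eliminate if # of DLT" reads 3, 4, 6, 7, 8 for 3, 6, 9, 12 and 15 patients treated at that dose. Rule (b) under the table stops the trial, with no MTD selected, if the lowest dose is eliminated. Rule (d) covers the lowest dose when the counts call for de-escalation: "we will treat the new patients at the lowest dose unless the number of DLTs reaches the elimination boundary".

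The appendix headed 15.6 gives a common source for the rule and its performance: "Table 1 is generated with software R 3.4 with BOIN package 2.4", and "Operative characteristics of the study design are also generated with BOIN package". The boundary call and the simulation call ("get.oc(target = target, p.true = p1, ncohort = nc, cohortsize = cs, n.earlystop = nes, p.saf = sb", and so on) share the target of 0.3, 10 cohorts of 3, the 0.21 and 0.39 limits, the stop at 15 patients on a dose, and the extra-safety option switched off. Neither call passes an elimination cut-off, and the protocol states none elsewhere.

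Table 2 (Section 11.1.2) reports 1000 simulated trials per scenario. For scenario 6 it gives 35.8% selection of level 1, 0.5% of level 2, 11.3 patients on average and 63.7% early stopping.

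**The concern.** If one setup produced both tables, running Table 1 should return Table 2 within simulation error. In the scenarios where elimination matters, it does not.

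The entry at issue is a safety boundary in a first-in-human trial. At 250 mg, 5 DLTs in 9 patients would end the trial under one version of the rule. Under the printed version, rule (d) keeps new patients coming at that dose. Anyone judging the protection from Table 2 is reading the performance of a stricter rule than the one in Table 1.

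**Working it through.** **Inputs.** The integer rows of Table 1; 10 cohorts of 3; stop at 15 on a dose; maximum 30; start at level 1, the set-up that reproduces Table 2; true DLT rates and stated results from Table 2. No elimination cut-off has to be assumed for the main comparison.

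**Reading Table 2.** The extracted table is broken, but scenario 6 is internally consistent: 100 − (35.8 + 0.5) = 63.7, and 10 + 1.3 = 11.3 patients. Early stopping there is therefore the share of trials with no dose selected. The same subtraction for scenario 3 gives 100 − (73.1 + 18.2 + 0.3) = 8.4%, with 20.1 patients stated. One selection cell is missing in that row; it belongs to a dose with a true DLT rate of at least 75%, beside cells of 0.

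**Escalation rows.** With φ = 0.30, φ₁ = 0.21, φ₂ = 0.39:

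- λₑ = ln[(1−φ₁)/(1−φ)] / ln[φ(1−φ₁)/(φ₁(1−φ))] = 0.2532
- λ_d = ln[(1−φ)/(1−φ₂)] / ln[φ₂(1−φ)/(φ(1−φ₂))] = 0.3441

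Escalating at or below λₑ and de-escalating at or above λ_d reproduces every escalate and de-escalate entry in Table 1. Only the elimination row is in question.

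**Simulation**, 300,000 trials per rule. z is the stated value minus the simulated value, divided by the standard error for 1000 trials.

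| | Stated or implied | Eliminate at 6/9 (printed) | Eliminate at 5/9 |
|---|---|---|---|
| Scenario 6, stopping | 63.7% | 59.0% (z = 3.0) | 63.2% (z = 0.3) |
| Scenario 6, mean patients | 11.3 | 12.01 (z = −3.6) | 11.36 (z = −0.3) |
| Scenario 3, no dose selected | 8.4% | 6.5% (z = 2.4) | 8.5% (z = −0.1) |
| Scenario 3, mean patients | 20.1 | 20.45 (z = −1.9) | 20.13 (z = −0.2) |

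For example, scenario 6 under 6/9: (0.637 − 0.590)/√(0.590 × 0.410/1000) = 3.0. Treating the two scenarios as independent runs, the stopping rates favour 5/9 over 6/9 by a likelihood ratio of about 1,350.

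**Check by hand, scenario 6.** At a 50% DLT rate, nine patients reach exactly 5 DLTs without earlier elimination in 72 of 512 sequences, or 14.1%; the simulation also gives 14.1%. From 5/9 under Table 1:

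- elimination at 7/12 needs at least 2 DLTs in the next 3: probability 0.50
- otherwise elimination at 8/15: (1/8)(1/8) + (3/8)(1/2) = 13/64 = 0.20
- never eliminated: 1 − 0.50 − 0.20 = 0.30

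The loss in stopping is 0.141 × 0.30 = 4.2 points, which equals 63.2 − 59.0. Trials that pass 5/9 treat 3 or 6 more patients with equal probability, so the average added is about 0.141 × 4.5 = 0.63; the simulation gives 12.01 − 11.36 = 0.65.

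**Other scenarios** (40,000 trials per rule). In scenarios 1, 2, 4 and 5, stopping differs by at most 0.1 point and mean sample size by less than 0.2 patients. Correct-MTD selection is 0.6 to 1.2 points higher under 6/9.

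**Secondary check, on an assumption.** The documents give neither prior nor cut-off. With a uniform prior, the posterior probability that the DLT rate exceeds 0.30 is 0.992 at 3/3, 0.971 at 4/6, 0.953 at 5/9, 0.989 at 6/9, 0.938 at 6/12, 0.982 at 7/12 and 0.974 at 8/15. A cut-off of 0.95, or any value from about 0.938 to 0.953, gives 3, 4, 5, 7, 8. The printed row requires a cut-off between about 0.953 and 0.971.

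**The case against.** Only one stopping rate in Table 2 separates the rules directly. The scenario 3 figure is a subtraction from a row with a missing cell, and the point turns on a single digit printed once in machine-read text. These are fair cautions. Still, the missing cell is almost certainly near zero and cannot supply two points, nothing suggests the digit was misread, and scenario 6 alone puts the printed rule about 3 standard errors out on stopping and 3.6 on sample size.

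The consequence is also narrower than a bare statement of the mismatch suggests:

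- It needs an overtly toxic lowest dose, below the 500 mg at which the trial starts.
- The 30% never eliminated applies to the 14% of scenario 6 trials that reach 5/9 at 250 mg, so about 4% of all trials in that scenario. Those trials still end at 15 patients on the dose, which limits further exposure there to six.
- Section 4.4 has the sponsor or its designee assign the dose, and Section 7.5 mentions review by a safety committee. Table 1 is not applied by sites alone.
- At higher levels, 5/9 under Table 1 leads to de-escalation but leaves the dose open to re-entry. That matters only where counts land on 9. If a level's single accelerated-phase patient is counted with later cohorts of three, its counts run 4, 7, 10, 13 and miss that column.

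All of this limits the size. None of it reconciles the two tables or supplies the missing cut-off.

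The level-2 start is not an explanation either: starting there in threes, the printed rule gives 57.9% stopping and 15.6 patients in scenario 6.

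**Conclusion.** The point holds. The printed elimination boundary at 9 patients and the stated stopping rates do not come from the same rule; Table 2 fits elimination at 5 in 9. Under Table 1 as printed, stopping in scenario 6 is about 59% rather than 63.7%, and a dose with a 50% DLT rate is selected in about 40% of trials rather than 35.8%. In scenario 3, no dose is selected in about 6.5% rather than 8.4%. MTD selection in the other scenarios is little affected.

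The comparison rests on the Table 1 integers, the Table 2 results, and a level-1 start in cohorts of three. The documents do not show which table reflects the intended rule. A uniform prior with a 0.95 cut-off would point to 5, but that is an assumption. This should be fixed because it concerns a stopping boundary, although its effect is modest.

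**What to change.** Choose one of two corrections:

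1. Change the n = 9 elimination entry in Table 1 to 5. This costs one cell, and Table 2 can stay.
2. Keep 6, state the cut-off that produces it, pass that cut-off in both script calls, and re-issue Table 2. Expect about 4 points less stopping in scenario 6 and 2 points less in scenario 3. This costs one re-run.

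In either case, add a sentence beside Table 1 giving the prior and the numerical cut-off.

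Also label Table 2 as simulated from level 1 in cohorts of three. The actual start is 500 mg, "which is at dose level 2 and approximately equal to 1/6 of human equivalent dose", with single patients first, so correcting the cell does not make 63.7% the stopping rate of the trial as run. A level-2 start in threes gives roughly 62% under 5/9 and 58% under 6/9, and neither figure includes the single-patient phase.

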**Figure 1. A hypothetical chart of dose escalation and de-escalation.**

The number indicates the enrolled patient number. Each circle represents one patient. A square box indicates a cohort. Dotted arrow indicates the lowering to next lower dose if a patient experiences DLT in previous infusions. Open cycle indicates no DLT during the 1st cycle of therapy. Gray cycle indicates grade 2 toxicities during the first cycle. Filled cycle indicates DLT during the first cycle of treatment.

## 1. BACKGROUND INFORMATION AND SCIENTIFIC RATIONALE

### 1.1. Background Information

Angiogenesis plays an important role in cancer development. More than a dozen different proteins have been identified as angiogenic activators, including vascular endothelial growth factor (VEGF), basic fibroblast growth factor, angigenin. The VEGF family and their receptors (VEGFR) are well characterized for their role in neoplastic angiogenesis. The best known monoclonal antibody targeting angiogenesis is bevacizumab (Avastin®). Bevacizumab has been approved for multiple cancers, including lung, ovarian, colorectal and brain cancer (<https://www.avastin.com>). Among them, VEGFR2 belongs to type V receptor tyrosine kinase encoded by KDR gene, and is expressed in vascular endothelial cells. It is a primary responder to vascular endothelial growth factor signal that regulates endothelial migration and proliferation. The expression of VEGFR2 can be found in multiple tumor types, including angiosarcoma, Kaposi sarcoma. In epithelial carcinoma, VEGFR2 expression can be found in mesothelioma, non-small cell lung cancer, and embryonal carcinoma[7]. The tissue levels of VEGF-C and VEGFR2 significantly correlate with the progression and prognosis of cancer.[8]

Targeting angiogenesis using either small molecule inhibitors or biological agents have been widely used in current cancer management. Current approved anti-angiogenesis biological agents include bevacizumab, ramucirumab, afibbercept. Among them, ramucirumab (IMC-1121B) targets vascular endothelial growth factor receptor 2 (VEGFR2). Ramucirumab has been approved for use in combination with paclitaxel for second-line treatment of patients with advanced gastric or gastroesophageal junction adenocarcinoma[9].

Ramucirumab is a fully human IgG1 monoclonal antibody that binds with high affinity to the extracellular domain of VEGFR2. It was discovered from an antibody phase display library from pooled B lymphocytes of healthy human donors. The EC50 of ramucirumab is approximately 0.15 nM. A crystal structure analysis demonstrates the binding of its Fab to domain 3 of VEGFR2 near N-terminus. It blocks the VEGF signaling by both steric blocking of its ligand and changing the receptor conformation[9].

### 1.2. Rationale to develop new anti-VEGFR2 monoclonal antibody

Although ramucirumab has been approved for gastric cancer, its improvement in overall survival is still not satisfactory. It prolongs the overall survival by 6 weeks when combined with paclitaxel. So far, there is not biomarker available to predict the efficacy of ramucirumab.

Therefore, a new monoclonal antibody also targeting VEGFR2 might provide better efficacy for cancer patients.

HLX06 is a new monoclonal antibody targeting VEGFR2. It has better binding affinity to VEGFR2, and also binds to different region in VEGFR2. *In vitro* studies have demonstrated the growth inhibition of human endothelial cells, and HLX06 has shown growth inhibition of tumors in xenogeneic studies.

Nonclinical studies up to weekly 150 mg/kg in *cynomolgus* monkeys for 13 weeks have shown good tolerability without evident toxicities (please refer to Investigator's brochure). HLX06 shows cross-reactivity to both monkey and human VEGFR2, but does not bind rodent VEGFR2.

This study is the first-in-human study to address the safety and tolerability of HLX06 in patients with metastatic or recurrent cancer.

### **1.3. Potential Risk and Benefits**

#### **1.3.1. Known potential risks**

HLX06 has not been tested in human before and its potential toxicities are unknown. Based on the nonclinical studies, HLX06 reacts with human and monkey VEGFR2, but not murine VEGFR2, so its prediction of toxicities in human is based on the monkey study with limited numbers. However, HLX06 is not the first monoclonal antibody targeting VEGFR2 to go into humans. Ramucirumab, a VEGFR-2 monoclonal antibody, has been widely used in different cancers with more than 1000 patients. When ramucirumab is used alone in a patient population similar to this study, the most common toxicity is grade-3 hypertension.[10] No increased risk of bleeding, venous thrombosis, proteinuria, or gastrointestinal perforation occurred[9]. However, when ramucirumab is used in combination with cytotoxic agents, it has a different toxicity profile. In the study with paclitaxel, the most common grade-3 or higher toxicities are neutropenia, leucopenia, hypertension, fatigue and abdominal pain.[11] When ramucirumab is used with FOLFOX chemotherapy as first-line therapy for colorectal cancer patients, the most common grade-3 or higher toxicities are neutropenia, fatigue, and neuropathy[12]. Based on the same target and similar mode of action by HLX06 in cancer cells, we expect the toxicity profile is likely to be similar to those observed in ramucirumab monotherapy. Although ramucirumab appears to be more tolerable than bevacizumab, Investigators have to remain vigilant given that no prior safety data are available for HLX06.

